#### 2.3.9 Rescue Medications

No rescue medications will be used during this study.

### 2.4 STUDY ENDPOINTS

### 2.5 STATISTICAL ANALYSIS

#### 2.5.1 Sample Size Determination

This pilot study aims to assess the feasibility of conducting a future clinical trial. Thus, the sample size of 30 patients was determined based on clinical and logistical reasons rather than statistical requirements. For Aim 1, we anticipate identifying approximately 300 potentially eligible patients during the 13.5 months of recruitment (~22 per month). A 95% confidence interval (CI) for the randomization rate provides a 3% margin of error (MoE) assuming the true rate was 10% (~3 per month). If the underlying dropout and adherence rates were 80%, a sample size of 30 provides 14% MoE for 95% CIs. For Aim 2, our sample size provides 83% power to detect a standardized mean difference of 0.65 for our efficacy outcomes. We are not powered to detect smaller effect sizes. However, since this is a proof-of-concept study, detecting a moderate-to-large effect size increases our confidence in the potential efficacy of urea. For Aim 3, underlying adverse events rates of 5% to 10%, 95% CIs will provide 8% to 11% MoE, respectively.

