# 1. OBJECTIVE, SPECIFIC AIMS, BACKGROUND, AND SIGNIFICANCE

# **1.1 OBJECTIVE**

## **Primary:**

- a. To determine the number and proportion of patients with chronic hyponatremia due to SIADH who met inclusion/exclusion criteria and were enrolled in the study.
- b. To determine the number and proportion of enrolled patients with chronic hyponatremia due to SIADH who completed the study.
- c. To determine the monthly enrollment rate of patients with chronic hyponatremia due to SIADH who met inclusion/exclusion criteria.
- d. To determine the number of prescribed urea doses taken by patients with chronic hyponatremia due to SIADH at completion of the study.
- e. To determine the reasons for non-adherence to urea therapy by patients with chronic hyponatremia due to SIADH.
- f. To assess the change in percentage accuracy action boundary selection in patients with chronic hyponatremia due to SIADH from baseline to day 42 of urea therapy
- g. To assess the change in overall score of sensorimotor ability battery in patients with chronic hyponatremia due to SIADH from baseline to day 42 of urea therapy.
- h. To assess the change in the sample entropy of the center of pressure data from the force plate in patients with chronic hyponatremia due to SIADH from baseline to day 42 of urea therapy.
- i. To assess the change in percentage angular deviation of vestibular control system using dynamic representation of upright stance in patients with chronic hyponatremia from SIADH from baseline to day 42 of urea therapy.
- j. To assess the change in percentage angular deviation of somatosensory control system using dynamic representation of upright stance in patients with chronic hyponatremia due to SIADH from baseline to day 42 of urea therapy.

- k. To assess the change in percentage angular deviation of visual control system using dynamic representation of upright stance in patients with chronic hyponatremia due to SIADH from baseline to day 42 of urea therapy.
- I. To assess the change in percentage weight symmetry using dynamic representation of upright stance in patients with chronic hyponatremia due to SIADH from baseline to day 42 of urea therapy.
- m. To assess the change in movement latency of posture control and stability using dynamic representation of upright stance in patients with chronic hyponatremia due to SIADH from baseline to day 42 of urea therapy.

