- n. To assess the change in amplitude scaling of posture control and stability using dynamic representation of upright stance in patients with chronic hyponatremia due to SIADH from baseline to day 42 of urea therapy
- o. To determine the number and proportion of patients with chronic hyponatremia due to SIADH enrolled in the study with adverse events related to the use of urea
- p. To determine the presence and nature of adverse events in patients with chronic hyponatremia due to SIADH related to urea therapy.

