## **1.2 SPECIFIC AIMS**

Hypotheses:

- a. We hypothesize that we will be able to recruit at least 10% of eligible patients with chronic hyponatremia due to SIADH.
- b. We hypothesize that we will be able to document at least 80% compliance with prescribed urea doses in patients with chronic hyponatremia due to SIADH.
- c. We hypothesize that urea will significantly increase the plasma sodium concentration at day 42 compared with the baseline level in patients with chronic hyponatremia due to SIADH.
- d. We hypothesize that urea will significantly improve the scores on neurocognitive and posture control and stability assessments at day 42 compared with the baseline scores in patients with chronic hyponatremia due to SIADH.
- e. We hypothesize that adverse events related to the use of urea in patients with chronic hyponatremia due to SIADH will be very uncommon.

Specific Aims:

Primary:

- 1. To assess the feasibility of recruiting patients with chronic hyponatremia due to SIADH into a study of oral urea and to evaluate their adherence to oral urea.
- 2. To assess the effect of oral urea on plasma sodium concentration and on neurocognitive function and postural control and stability in patients with chronic hyponatremia due to SIADH.
- 3. To explore the safety of oral urea in patients with chronic hyponatremia due to SIADH.

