## 2. RESEARCH DESIGN AND METHODS

### 2.1 CLASSIFICATION AND METHODOLOGICAL DESIGNS

The proposed pilot study is designed as a prospective, cross-over trial. Over a 13.5-month period, we will recruit 30 outpatients with chronic non-severe hyponatremia (PNa 125 to 132 mmol/L) confirmed to be due to SIADH. Subjects will not be withdrawn from any known effective therapy for chronic hyponatremia for the purpose of participating in this study. Following enrollment, patients will be randomly assigned on 1:1 ratio to one of two sequence groups. Patients assigned to group "Urea ON, then Urea OFF" will receive oral urea for 42 ± 3 days (period 1), followed by a 10 ± 4-day period in which all patients will be off urea (washout period). Patients then will be off urea for 42 ± 3 days (period 2). Patients assigned to group "Urea OFF, then Urea ON" will be off urea therapy for 42 ± 3 days (period 1), and following a 10 ± 4-day washout period then they will initiate urea for 42 ± 3 days (period 2). Patients will have PNa assessed at baseline and on days 7 ± 2, 14 ± 2, and 42 ± 3 during periods 1 and 2 of the study and will undergo neurocognitive and postural control and stability testing on days 0 and 42 of each of the study periods. All patients will be advised to restrict their fluid intake to ≤1.2 liters during periods 1 and 2.

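### Section 2.5.1 equates a 10% randomization rate with about 3 patients per month, but its own inputs give about 2.2; the adverse-event precision would also be clearer as exact limits (optional)

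*Combined protocol and SAP*

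**What the plan says.** **Recruitment.** Section 2.5.1 anticipates "approximately 300 potentially eligible patients during the 13.5 months of recruitment (~22 per month"). It continues: "A 95% confidence interval (CI) for the randomization rate provides a 3% margin of error", "assuming the true rate was 10% (~3 per month"). Section 2.1 sets the target: "Over a 13.5-month period, we will recruit 30 outpatients with chronic non-severe hyponatremia". Hypothesis (a) in section 1.2 is that "we will be able to recruit at least 10% of eligible patients". Primary objective (c) in section 1.1 is "To determine the monthly enrollment rate of patients with chronic hyponatremia due to SIADH", and the synopsis lists the monthly rate as primary endpoint 3.

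**Adverse events.** Section 2.5.1 also states: "For Aim 3, underlying adverse events rates of 5% to 10%, 95% CIs will provide 8% to 11% MoE, respectively". The quantity concerned is primary objective (o), the number and proportion of patients "enrolled in the study with adverse events related to the use of urea". No interval method is named in section 2.5.1 or in section 2.5.4 (Safety Analysis).

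**The concern.** The monthly figure and the percentage in one sentence are meant to be the same quantity on two scales, and they do not agree. The pilot exists to inform a larger trial, and section 2.5.2 says that achievement of the aims, including the target number of patients, will be assessed at the end. A study that met its plan exactly (30 patients, 10%, 13.5 months) would enroll 2.2 per month and look about 26% short of the printed figure (2.22/3 = 0.74).

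The adverse-event margins raise a different and smaller question. At rates of 5% to 10% with 30 patients only 1.5 to 3 events are expected. A symmetric margin describes precision poorly there, and the upper limit is the figure that bears on the hypothesis that urea-related events are very uncommon.

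**Working it through.** **Inputs.** 300 potentially eligible patients, 13.5 months, 10% randomization rate, 3% margin, 80% for dropout and adherence, adverse-event rates of 5% and 10% (all section 2.5.1); 30 patients in 13.5 months (section 2.1); replacement of withdrawn patients (sections 2.3.6 and 10).

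**Monthly rate**

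- Identified per month: 300/13.5 = 22.2. The plan's 22 reproduces.
- Randomized per month at 10%: 0.10 × 22 = 2.2.
- Randomized per month from the target: 30/13.5 = 2.22.
- What 3 per month implies: 3 × 13.5 = 40.5 patients, and 40.5/300 = 13.5%.

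**Which figure is out of line?** The margin in the same sentence settles it. With half-width 1.96 × √(p(1−p)/300):

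| Randomization rate | Margin |
|---|---|
| 10% | 3.39%, rounds to 3% as printed |
| 12.5% | 3.74%, rounds to 4% |
| 13.5% | 3.87%, rounds to 4% |

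The 10%, the 3% margin and the target of 30 agree with one another. Only the monthly figure does not fit.

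**Could replacement of withdrawn patients explain it?** Reading the 80% in section 2.5.1 as 80% retention (an assumption) and replacing every leaver: 30/0.8 = 37.5 enrollments; 37.5/13.5 = 2.78 per month; 37.5/300 = 12.5%. That comes close to 3, but at 12.5% rather than the stated 10%.

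**Aim 3 margins.** The plan's figures reproduce as symmetric (Wald) half-widths at n = 30:

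- 1.96 × √(0.05 × 0.95/30) = 7.8%, interval −2.8% to 12.8%
- 1.96 × √(0.10 × 0.90/30) = 10.7%, interval −0.7% to 20.7%

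Upper 95% limits for whole counts out of 30:

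| Affected | Wald | Exact (Clopper-Pearson) | Wilson |
|---|---|---|---|
| 0 | zero width | 11.6% | 11.4% |
| 1 | 9.8% | 17.2% | 16.7% |
| 2 | 15.6% | 22.1% | 21.3% |
| 3 | 20.7% | 26.5% | 25.6% |

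The corresponding exact lower limits are 0, 0.1, 0.8 and 2.1%.

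Coverage of the nominal 95% Wald interval, summed over Binomial(30, p), is 78.2% at a true rate of 5% and 80.9% at 10%. Nearly all the misses are on the upper side: at 5% from 0/30 (0.95^30 = 21.5%), at 10% from 0/30 and 1/30 (18.4% together). Coverage is uneven in between: 94.7% at 9.7%, and 88% on average over 5% to 10%.

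**If the number exposed is not 30.** Assumed range: 27 (20% of the 15 patients who start off urea leave before receiving it and are not replaced, 30 − 3) to 38 (20% of those enrolled leave after exposure and all are replaced, 30/0.8 = 37.5). Exact upper limits for 0, 1, 2 and 3 affected are 12.8, 19.0, 24.3 and 29.2% at 27, and 9.3, 13.8, 17.7 and 21.4% at 38.

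**The case against.** **On the monthly figure.** It is a parenthesis marked as approximate, and 2.2 rounded up to a whole patient is 3. That reading is weak, because the same paragraph writes 22.2 as about 22, and the same rounding would give about 2. It is also fair to say that nothing is calculated from the figure, that the sample size was set on clinical and logistical grounds, and that a reader can derive the right pace from section 2.1. Those points stand. They limit the weight of the correction without making the figure right.

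**On the adverse-event limits.** The margins are correct as planning figures, and the plan does not commit to Wald intervals for the report, so the coverage result is no criticism of a declared method. Exact limits err the other way: at n = 30 they cover 98.4% at a true 5% and 99.2% at 10%, so part of the gap from Wald is their own conservatism. Wilson limits are less conservative and still well above Wald (25.6% against 20.7% for 3/30). The low end of the exposure range assumes that some leavers are not replaced, although sections 2.3.6 and 10 say withdrawn patients will be; both ends are illustrations only. The plan also says it is not designed to identify low-frequency events comprehensively, and no decision rule uses the margin. All of this stands, and it is why this part is a suggestion.

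**Conclusion.** The monthly figure in section 2.5.1 is wrong as written: the inputs give 2.2 per month, not about 3, or 30 patients rather than about 40 over the recruitment period. This follows from the document's own numbers without outside assumptions; only the test of the replacement explanation relies on reading 80% as retention. The consequence is small, because the sample size, the 10% hypothesis and the 3% and 14% margins for Aim 1 are unaffected.

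The Aim 3 margins are not an error. Restating them as exact or Wilson limits is a gain in clarity only. The limits quoted for 30 patients assume that exactly 30 are exposed to urea.

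**What to change.** 1. In section 2.5.1, change the monthly randomization figure to about 2.2 per month. If enrollment of replacements is meant to be included, give that as a separate figure with its assumed dropout.
2. Optional: replace the Aim 3 sentence with wording such as: *If 30 patients are exposed to urea and 0, 1, 2 or 3 are affected, the exact 95% CIs are 0–11.6%, 0.1–17.2%, 0.8–22.1% and 2.1–26.5%. Adverse-event proportions will be reported with exact or Wilson limits, using the actual number exposed as the denominator.* Choose one of the two methods when finalizing the text.

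The cost is one number and, if the option is taken, one sentence. Visits and data collection do not change. The only drawback of the second change is that the stated adverse-event precision will look less favourable.

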## 2.5.2 Study Conduct Analysis

At the conclusion of the study, we will assess the achievement of our aims including the target number of patients.

#### 2.5.3 Efficacy Analysis

This study is not powered to establish the efficacy of urea on increasing PNa or improving neurocognition and/or postural control/stability. However, to justify a future large, randomized clinical trial of urea, we need proof of concept data that urea has potential benefits for these outcomes. We will summarize patient demographics and clinical characteristics by study group. For the primary outcomes (PNa, neurocognition scores, postural control/stability scores) and secondary exploratory outcome (SF-12 scores), we will calculate change from baseline to day 42 in each treatment period. We will analyze these data using a linear mixed effects model with patient-specific random effects to account for within-patient correlations. Model predictors will include treatment,

period and treatment period interaction. Coefficients and 95% CIs will be used to quantify the treatment effect. We will also use this model to assess period effect and carryover effects (treatment period interaction).

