as the sole drug therapy for hyponatremia ('urea-only' patients). Overall, 58 patients received urea (7.5-90 g/day) over a median of 4.5 days and demonstrated an increase in PNa from 124 to 131 mmol/L (p<0.001). Among 12 'urea-only' treated patients, PNa increased from 125 to 131 mmol/L (p=0.001) with a larger increase in PNa by 24 h (2.5 mmol/L [IQR 0-4.5] vs. -0.5 mmol/L [IQR -2.5 to 1.5], p=0.04) and more patients normalized PNa (33% vs. 8%, p=0.08) compared to a control group. No patients experienced overly rapid correction of PNa and no serious adverse events were reported. While our study was retrospective and limited to hospitalized patients, the findings support the potential efficacy and safety of this agent. After the publication of our study, two other observational studies were published supporting the efficacy, safety, and tolerability of oral urea in hyponatremia.(28, 29) Just one past study compared urea to other therapies for hyponatremia. Soupart et al. compared urea to vasopressin antagonists in 13 patients with chronic SIADH.(30) Patients were treated with vaptans (satavaptan and tolvaptan) for 1 year, during which PNa increased from 125±3 mmol/L to 135±3 mmol/L. Vaptans were then discontinued, leading to recurrent hyponatremia. After an 8-day washout period, oral urea was prescribed for 1 year with normalization of PNa in all patients (mean PNa 135±2 mmol/L). Patients tolerated urea well with no significant side effects. To date, there have been no studies comparing urea to fluid restriction.

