- A co-investigator will test patients' balance while standing on a specialized piece of equipment. Patient will be asked to stand on both legs on top of a platform in a dynamic moving environment. Patient will go through six conditions, with three trials per condition, lasting about 20 seconds each. Patient will be asked to look forward, and stand as motionless as possible with your arms at your sides. The six conditions include the possibility of moving surroundings or moving base of support. If patient move or lose his/her balance during the procedures, patient will be asked to repeat that part again. Patient will be supported by means of a harness in the equipment to make sure he/she cannot fall over while performing the tests.
- The research coordinator will instruct the patient to restrict his/her fluid intake to no more 1200 mL/day for the next 42 ± 3 days. The research coordinator will provide the patient with a diary to record daily fluid intake.
- Patients will be randomized prior to or at the first study visit (Period 1 Day 0) following completion of baseline assessments. Our biostatistician will generate the randomization list using permuted blocks of random block sizes of 4 and 6 and our systems analyst will load the list into RedCAP. To preserve allocation concealment for consecutively enrolled participants, we will use the randomization module in RedCAP to assign each participant 1:1 to either On-to-Off Urea sequence or Off-to-On Urea sequence.
- If patient is randomized to take On-to-Off Urea sequence then the research coordinator will give the patient 48 urea powder pouches with instructions on how to take the urea every day. The research coordinator will provide the patient with a diary to record patient's daily urea intake.
- This visit will last approximately 2.5 hours.

Second study visit (Day 7 of Period 1)

- The research coordinator will call the patient on the phone to ask some questions about any new symptoms patient might have experienced since his/her last visit.
- The research coordinator will direct the patient to go the UPMC clinical laboratory of the patient's choice that day to have his blood drawn for analysis of a basic metabolic panel.
- If patient is taking urea, we might call the participant on the phone again to ask to change the dose of urea depending on the sodium level results.
- This visit will last approximately 20 minutes.

Third study visit (Day 14 of Period 1)

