- The research coordinator will draw approximately 14 mL of patient's blood and send the specimen promptly to the UPMC Presbyterian clinical laboratory for processing and analysis of the following: basic metabolic panel, plasma osmolality, and plasma uric acid.
- Patient will complete the SF-12 survey with pen and paper.
- A co-investigator will test patients' reactions and decision making using specialized software on a tablet computer.
- A co-investigator will test patients' balance while standing on a specialized piece of equipment. Patient will be asked to stand on both legs on top of a platform in a dynamic moving environment. Patient will go through six conditions, with three trials per condition, lasting about 20 seconds each. Patient will be asked to look forward, and stand as motionless as possible with your arms at your sides. The six conditions

include the possibility of moving surroundings or moving base of support. If patient move or lose his/her balance during the procedures, patient will be asked to repeat that part again. Patient will be supported by means of a harness in the equipment to make sure he/she cannot fall over while performing the tests.

- The research coordinator will ask patient to stop fluid restriction.
- If patient is taking urea then the research coordinator will instruct the patient to stop taking urea and return all the urea pouches he/she did not use to the research coordinator.
- The research coordinator will provide the patient with a container with instructions to collect urine for 24 hours prior to next study visit.
- This visit will last approximately 2.5 hours.

Reminder telephone call

• The research coordinator will call the patient on the phone 48-72 hours before the next study visit to remind him/her of the upcoming study visit.

Fifth study visit (Day 0 of Period 2)

- Patient will come in person to the University of Pittsburgh Neuromuscular Research Laboratory located at [name].
- Patient will bring the container with the 24-hour urine collection he/she started the day prior. The research coordinator will send the specimen promptly to the UPMC Presbyterian clinical laboratory for processing and analysis of the following: creatinine, urea nitrogen, uric acid, osmolality, sodium, and potassium.

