# **3.2 INCLUSION CRITERIA**

- a. Age ≥18 years
- b. Attended ≥1 visit at a UPMC outpatient clinic within the prior 12 months
- c. Chronic hyponatremia with a history of ≥ 2 sequential plasma sodium concentration (PNa) between 125 mmol/L and 132 mmol/L performed ≥ 14 days apart within the last 18 months with most recent PNa ≤ 132 mmol/L prior to screening
- d. Patients are ambulatory without the need for any assist device (e.g., cane, walker)
- e. Mini-mental state examination (MMSE) score  $\geq$  25
- f. Diagnosis of SIADH established by the Bartter and Schwartz criteria as follows:
  - Hyponatremia with a PNa between 125 mmol/L and 132 mmol/L
  - Plasma osmolality < 275 mOsm/kg
  - Clinical euvolemia
  - Urine osmolality > 100 mosm/kg
  - Urine Na ≥ 20 mmol/L
  - Intact adrenal function (i.e., morning plasma cortisol value ≥15 µg/dL, or negative corticotropin stimulation test)
  - Normal thyroid stimulating hormone level (i.e., TSH between 0.3 to 5 µIU/mL)
  - eGFR ≥ 45 ml/min/1.73 m2)

g. Nephrology patients who meet eligibility for the study including a nadir serum sodium of no less than125 mmol/L and have already started urea and treating physician agrees to discontinuing prescribed urea.

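### Section 2.5.3 analyses raw change with no day-0 covariate and does not name the efficacy contrast; fixing both costs little and may narrow the ON-minus-OFF interval

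*Combined protocol and SAP*

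**What the plan says.** For the efficacy outcomes (PNa, neurocognition, postural control and stability, SF-12), section 2.5.3 states: "we will calculate change from baseline to day 42 in each treatment period". The model is a linear mixed model with patient random effects. Its predictors are treatment, period and treatment-by-period, with no baseline value among them. The result is described as follows: "Coefficients and 95% CIs will be used to quantify the treatment effect". No contrast or coding is named. The interaction stays in that model for a further purpose: "We will also use this model to assess period effect and carryover effects (treatment period interaction").

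The day-0 data exist in both periods. Section 2.1 schedules functional "stability testing on days 0 and 42 of each of the study periods", and Table 1 and the visit list in section 2.2 place PNa and SF-12 at day 0 as well.

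Section 2.5.3 does not define baseline. Section 2.2 uses the word for the day-0 assessments, and the first-visit text places randomization before or "at the first study visit (Period 1 Day 0) following completion of baseline assessments". The natural reading for the analysis is each period's own day 0.

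Section 2.5.1 gives 30 patients and 83% power at a standardized mean difference of 0.65. It states no SD, within-patient correlation or alpha for that figure.

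**The concern.** There are two separate issues.

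- **Precision.** Subtracting day 0 in full is the best use of it only when the regression of the day-42 ON-OFF difference on the day-0 ON-OFF difference has slope 1. At a smaller slope, raw change carries day-0 noise into the estimate. A covariate lets the data set the weight.
- **Which number is reported.** In a model with a treatment-by-period term, the meaning of the treatment coefficient depends on the coding. Under reference coding it is the treatment difference in the reference period, which is a between-patient comparison. Under sum-to-zero coding it is the average over both periods.

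The ON-OFF interval is the proof-of-concept result meant to justify a larger trial. With 30 patients, avoidable width matters. So does a plan from which two analysts could report different effects from the same data.

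**Working it through.** **1. The plan's own figure.** Noncentral t, two-sided 0.05 (assumed), difference 0.65:

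- Within-patient, n = 30, 28 df, 0.65 in SDs of the within-patient difference: 93%.
- 15 v 15, two-sample: 40%.
- 0.65 in raw outcome SDs, within-patient correlation 0.30, n = 30: 82.7%.

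The stated 83% therefore needs an input that the plan does not give. It is neither confirmed nor shown wrong, and the point does not rest on it.

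**2. Precision formula.** Assumptions: day-42 SD is 1, day-0 SD is s, the within-period correlation is r1, and every cross-period correlation is r2. Let k = (r1 - r2)/(1 - r2). Per patient, for the ON-OFF difference:

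- raw change: Var = 2(1 - r2)(1 + s² - 2sk)
- adjusted for day 0: Var = 2(1 - r2)(1 - k²)

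Estimating the slope with 30 patients inflates the adjusted variance by about 1 + 1/26 = 1.038. So the ratio of raw to adjusted variance is (1 + s² - 2sk)/(1 - k²)/1.038, and relative CI width is its square root.

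**3. Equal SDs (s = 1).** Example with r1 = 0.7, r2 = 0.5: k = 0.2/0.5 = 0.4, and (2 - 0.8)/(1 - 0.16)/1.038 = 1.38.

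| r1, r2 | k | variance ratio | raw CI wider by |
|---|---|---|---|
| 0.6, 0.6 | 0 | 1.93 | 39% |
| 0.6, 0.5 | 0.20 | 1.60 | 27% |
| 0.8, 0.7 | 0.33 | 1.44 | 20% |
| 0.7, 0.5 | 0.40 | 1.38 | 17% |
| 0.8, 0.5 | 0.60 | 1.20 | 10% |
| 0.8, 0.3 | 0.71 | 1.12 | 6% |
| 0.9, 0.5 | 0.80 | 1.07 | 3% |

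The 3% is not a floor. At s = 1 the ratio simplifies to 2/(1 + k)/1.038, so the gain vanishes as k approaches 1. Simulation of 20,000 trials with 15 per sequence gave 1.94 (0.6, 0.6), 1.36 (0.7, 0.5) and 1.20 (0.8, 0.5). Null rejection was 4.8% to 5.2% for both methods, so both tests are valid.

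**4. Smaller day-0 SD (s = 0.5 to 0.7; r1 0.6-0.8, r2 0.5-0.7).** The ratio runs from 0.96 to 1.43, so the raw CI is between 2% narrower and 20% wider. The worst case is s = k, where the ratio is 1/1.038 = 0.96. With 24 completers the loss is about 3% in width.

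This case is possible for PNa because entry requires "Hyponatremia with a PNa between 125 mmol/L and 132 mmol/L"; a uniform spread over that range has SD 7/√12 = 2.02. The background does not settle it. One cited series reports "PNa increased from 125±3 mmol/L to 135±3 mmol/L" on vaptans and then 135±2 on urea. Another reports 128.8±3.9 to 133.5±3.5 under mixed non-urea treatment.

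**5. The contrast.** With 15 per sequence, the variance of the period 1 difference over that of the averaged raw-change contrast is

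2(1 + s² - 2s·r1) / [(1 + s²)(1 - r2) - 2s(r1 - r2)].

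- s = 1: 2(2 - 2r1)/(2 - 2r1) = 2.0 for any correlations, so the CI is √2 = 1.41 times as wide.
- s = 0.5, r1 = 0.8, r2 = 0.7: 2(0.45)/(0.375 - 0.10) = 0.90/0.275 = 3.27, so the CI is 1.81 times as wide.

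In fitted mixed models the reference-coded treatment coefficient equalled the period 1 group difference to within 5e-15.

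**6. How the covariate enters.** With all correlations 0.7 (40 simulated trials), the mean standard error was 0.186 for raw change. It was 0.163 with the day-0 value alone in a random-intercept model, and 0.142 when the patient mean and the within-patient deviation were entered separately. The patient mean is needed to recover the full gain.

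**The case against.** **Nothing in the plan is wrong.** Within-period change in a mixed model is a recognised crossover analysis, the study is a pilot, and section 2.5.3 disclaims power for efficacy. This stands, and it is why the point is only about efficiency and clarity.

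**The size rests on assumed correlations.** This also stands. The range depends on the settings chosen, and no particular gain can be presented as expected.

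**The period 2 day-0 value follows randomization and may hold carryover.** True, but raw change already uses that value at full weight. With a 0.3 SD carryover in that value only (r1 = 0.7, r2 = 0.5), the bias was 0.15 for raw change and 0.06 after adjustment.

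**Reference coding is not in the plan.** Correct. The patient random effects and the 83% power claim point towards a within-patient contrast, since 15 v 15 would give 40%. A reader might infer that the trial intends to report the period 1 comparison; the documents do not say so. What stands is that they do not exclude it.

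**The functional scores might seem the clear winners, having no entry limit of their own.** The documents do not support that inference. Entry requires an MMSE score of at least 25 and unaided walking, several impairing conditions are excluded, and no reliability figures are given for these tests.

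**Hypotheses c-d and the change objectives are worded as day 42 against baseline.** A reader might infer a pre-post test on urea. None is planned in section 2.5.3, so rewording them would be editorial only.

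**Conclusion.** The point holds as an optional improvement in precision and clarity. It would be too strong to call the planned estimate biased or its test invalid: absent carryover it is unbiased, and simulated type I error is nominal.

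- **Covariate.** At n = 30 with equal SDs, the raw-change interval is about 3% to 39% wider over the correlations tried. With a smaller day-0 SD the gain may be nil, and the worst-case loss from adjusting is about 2-3% in width. All of this is conditional on assumed correlations and SDs, and on reading baseline as each period's own day 0.
- **Contrast.** If software defaults to reference coding and that coefficient is reported, its variance is 2.0 to 3.3 times that of the averaged within-patient contrast. This is a risk left open by the wording, not the stated plan.

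**What to change.** Two changes in section 2.5.3:

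1. Define baseline as the same period's day 0 and keep change from it as the response. Add that period's day-0 value and the patient's mean day-0 value as covariates. For a patient with only one period, use the available day-0 value as the mean. With these covariates the treatment estimate is identical to that from modelling the day-42 value, so the listed change endpoints need not be altered.
2. State that the efficacy result is the ON-minus-OFF difference averaged over the two periods, with its 95% CI, taken as a contrast from the planned model. Use the treatment-by-period term only to assess carryover. No separate model is needed: in 20 balanced simulated trials the averaged contrast from the interaction model matched the no-interaction treatment estimate (difference below 1e-15, standard errors within about 2%).

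The cost is one or two degrees of freedom and a few sentences. No visit, sample or measurement is added. Aligning the wording of the hypotheses and objectives with ON minus OFF is optional.
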